5.2.4 SAFETY POPULATION

The safety population includes all subjects who were assigned a Tango Belt and attempted the run-in period.

6 GENERAL ISSUES FOR STATISTICAL ANALYSIS

Descriptive statistics for continuous variables will be summarized using descriptive statistics (number of subjects, mean, median, quartiles, standard deviation [SD], minimum, and maximum). Categorical variables will be summarized using frequencies and percentages of subjects in each category. All results will be presented by treatment and appropriate subject populations.

Statistical results such as confidence intervals and descriptive statistics for intervention primary effectiveness outcomes will be presented by site and in aggregate. Likewise, incidence of adverse events will be presented by site and in aggregate.

P-values will be one-sided and considered significant at the 0.025 level, or two-sided and considered significant at the 0.05 level of significance.

6.1 ANALYSIS SOFTWARE

Analysis data sets, statistical analyses and associated output generated by Avania will be generated using SAS® Software version 9.4 or later and/or R version 4.2.0 or later.

6.2 DISPOSITION OF SUBJECTS AND WITHDRAWALS

6.2.1 Intervention Population

The number and percent of subjects in each analysis population will be presented, with percentages based on the ITT population for the intervention group. The frequency and percent of subjects who

SAP: COP-0001 Active Protective Technologies, Inc

completed each scheduled assessment will be presented in a table. The number and percentage of ITT subjects prematurely withdrawing will be presented overall and by reason of discontinuation.

6.2.2 HISTORICAL CONTROL POPULATION

Due to the retrospective nature of the control group, only observed data will be used in analyses. Control subjects missing information will not be used in the Propensity Score (PS) analysis as there will be no imputation of missing data for the HC population.

6.3 METHODS FOR WITHDRAWALS AND MISSING DATA

All practical monitoring and follow-up steps will be taken to ensure complete and accurate data collection. Since endpoints are assessed at the 180-day visit, it is anticipated that there will be approximately 30% attrition. Given the disproportionately high rate of death and other loss-to-follow up reasons within this population, multiple imputation approaches will be carried out for missing primary endpoint data on the ITT population. The primary effectiveness analysis will be performed on data that has the primary outcome multiply imputed.

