4 SAMPLE SIZE

It is estimated that the sample size will include up to 268 subjects in the intervention group and up to 536 subjects in the historical control group. This estimated sample size includes the minimum sample size required to assess the primary endpoint with an additional 30% increase to account for possible subject attrition.

The sample size for the primary hypothesis will be calculated with 80% power. The annual rate of falls with major hip injury has been estimated between 6% and 10% in higher-risk populations within long-term care facilities. Since the fall rate is not exactly known in the study population, the fall rate observed in the historical control group, a nuisance parameter, will be used for sample size calculations. After roughly 70% of subjects were enrolled into the historical control group, the proportion of subjects who experienced a major hip injury due to a fall was calculated to be 15% and this rate was used in the sample size calculation.

The following steps were used to calculate the sample size (for further details, see section 10.1 of the Protocol):

1. Test the historical control time periods to determine if all the time periods can be used, depending on if any time periods differ in fall rate

- 2. From the remaining historical control data, the fall rate was calculated and the total sample size available for the historical control group
- 3. The sample sizes for the historical controls and the prospective Tango Belt arm at the interim analysis was calculated.
- 4. The sample size for the prospective Tango Belt arm at the final analysis was calculated using the total sample of historical controls.

This sample size determination was made based on the following specifications:

Primary Effectiveness Endpoint Assumptions:

The following assumptions were made for estimating sample size for the primary effectiveness endpoint:

- 1. Alpha of 0.025 (one-sided)
- 2. 80% power
- 3. Groups are independent

Based on the above assumptions, the minimum sample required for the intervention group for evaluation of effectiveness (unadjusted) is 94 subjects. At least 134 subjects will be enrolled to the intervention group to account for subject attrition and missing data (estimated to be 30%).

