4.1 INTERIM ANALYSES

The study will incorporate a group sequential design (GSD) in which an interim analysis will be performed to detect an 80% protective effect of the Tango Belt at 80% power. If a significant difference is found between the prospective Tango Belt subjects and historical controls at the interim analysis, the study will be stopped, and the Tango Belt deemed superior to SOC alone. If not, sample size reestimation will be completed, and enrollment will continue until a final sample size is reached to detect a 60% protective effect of the Tango Belt at 80% power and a 5% total level of significance.

Following the steps from section 4, we assumed subjects were followed for an average of 6 months, an annual fall-with-major-hip-injury rate of 15%, and sufficient historical control subjects to allow 1:2 allocation of subjects to treatment and control. This would require 134 subjects in the prospective Tango Belt group and 268 subjects in the historical control group at the interim analysis using the Pocock alpha-spending function as well as accounting for 30% attrition. At the end of the study (should the higher effectiveness target not be achieved at interim analysis), 268 total subjects would be required in the prospective Tango Belt group and 536 subjects would be in the historical control group.

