6.3.1 MULTIPLE IMPUTATION

Prior to propensity score matching, the intervention group may have missing information on the primary endpoint (i.e. major hip injury due to a fall), primarily due to premature withdrawal from the study.

At the time of the final analysis, if more than 20% of data is missing for the primary endpoint reported at the 180-day visit, then the primary endpoint will be multiply imputed and the analysis from section 7.2 will be repeated using both observed and multiply imputed data.

For the multiple imputation, a total of 50 imputed datasets will be calculated (Graham et al.). Fully conditional specification (FCS) logistic regression will be used to impute missing major hip injury due to a fall status (primary endpoint) using the baseline covariates of age, sex, ethnicity, race, mobility level (Independent, Limited Assist, Supervision, Extensive Assist, or Total Dependence), BIMS Score, and FES-I score.

The analysis for the primary endpoint will be carried out utilizing 50 datasets and then results will be combined using PROC MIANALYZE in SAS to obtain one overall test of significance.

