7.2 PRIMARY EFFECTIVENESS ANALYSIS

The primary effectiveness endpoint for this study is the proportion of subjects experiencing major hip injuries due to falls, as reported at the 180-day visit and will be presented for the Tango Belt and control groups using the ITT and adherence populations.

The proportion of subjects experiencing major hip injury due to falls is defined as the total number of subjects who experience a major hip injury due to a fall divided by the total number of subjects.

The primary effectiveness hypotheses are:

$$\begin{array}{l} H_0 \colon \pi_T \ \geq \ \pi_C \\ H_1 \colon \pi_T \ < \pi_C \end{array}$$

where π_T and π_C are the proportion of subjects experiencing major hip injuries due to falls in the Tango Belt and control group, respectively.

The null hypothesis (H_0) for this endpoint states that the true proportion of subjects using Tango Belt and experiencing major hip injuries due to falls is greater than or equal to the true proportion of subjects in the control group who experience major hip injuries due to falls. The alternative hypothesis (H_1) states that the true proportion of subjects using Tango Belt and experiencing major hip injuries due to falls is less than the true proportion of subjects in the control group who experience major hip injuries due to falls.

The proportion of major hip injuries by treatment group will be presented along with a 95% confidence interval using the Clopper-Pearson method. H_0 will be tested at a one-sided 0.025 level of significance using a logistic regression analysis to compare treatment groups while controlling for propensity score.

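### Belt subjects who die or leave uninjured have their 180-day status imputed from baseline covariates alone, controls are not imputed and the scoring of their exits is unstated: reported risks can be inflated, and the comparison is biased if the groups differ in attrition or in scoring

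*Combined protocol and SAP*

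**What the plan says.** - **Endpoint window.** SAP 3.2.1 counts major hip injuries reported from enrollment to the 180-day visit. SAP 6.3, 6.3.1 and 7.2 speak of assessment or reporting at the 180-day visit. SAP 7.2 defines the proportion as subjects with an injury "divided by the total number of subjects".
- **Belt group.** SAP 6.3 expects about 30% attrition, cites death and other loss to follow-up, and states that "multiple imputation approaches will be carried out for missing primary endpoint data on the ITT population". It makes the imputed analysis the primary one. SAP 6.3.1 describes the missing endpoints as "primarily due to premature withdrawal from the study". It imputes them by logistic regression on age, sex, ethnicity, race, mobility, BIMS and FES-I. Time on study and reason for exit are not in the model. It does this only at the final analysis, only if more than 20% is missing, and as a repeat of the analysis.
- **Controls.** SAP 6.2.2 says "only observed data will be used in analyses". Controls with missing information are left out of the propensity score analysis, and nothing is imputed.
- **What is absent.** Neither document gives a time-to-event, person-time or competing-risk analysis, or says how an uninjured death is scored.

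**The concern.** Take two belt subjects who both leave on day 60. The one injured on day 40 has a known endpoint. The one not injured is missing, although 60 injury-free days are on record. Missingness then depends on the outcome itself, and baseline covariates cannot correct for that. The model can also assign a later hip injury to a resident who died uninjured.

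The two groups are also handled by different rules. Only belt subjects consent and can withdraw voluntarily (protocol 5.3 and 5.4). The 30% figure was revised from belt-group exits (SAP 9), and no control figure is given. At stake are the per-group risks that SAP 7.2 will report and, if exits or their scoring differ between groups, the treatment comparison.

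**Working it through.** **1. Which 15%?** SAP 4 reports that "the proportion of subjects who experienced a major hip injury due to a fall was calculated to be 15" per cent, while SAP 4.1 calls 15% an annual rate over an average of 6 months. The sample size shows which was used.

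- Inputs: "The sample size for the primary hypothesis will be calculated with 80% power"; "Alpha of 0.025 (one-sided"); "an interim analysis will be performed to detect an 80% protective effect of the Tango Belt at 80% power"; 1:2 allocation; Pocock spending.
- One-sided alpha at half information: 0.025 × ln(1 + (e − 1) × 0.5) = 0.0155.
- Two-proportion formula with continuity correction, 3% against 15%: 94 belt subjects, as stated (82 without the correction). 94 / 0.7 = 134.3; the plan says 134.
- With 7.5% as the 6-month risk (1.5% against 7.5%), the same formula gives 198.

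The plan's figure therefore uses 15% as the 6-month risk. I use 15% below as an assumption and show 7.5% beside it.

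**2. Model.** Let p be the 180-day risk under constant hazard and a the share of subjects who exit, with exits uniform over 180 days and independent of injury. The mean risk before exit among leavers is

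q = 1 − p / (−ln(1 − p)).

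- p = 15%: q = 1 − 0.15/0.16252 = 0.0770
- p = 7.5%: q = 0.0380
- p = 6%: q = 0.0303

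**3. Risk in one group.** If injuries before exit count and event-free leavers are missing, dropping them gives

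P = [(1 − a)p + aq] / [(1 − a) + aq].

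Imputing from baseline covariates reproduces the same proportion on average, because the model is fitted to these same observed subjects.

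| Attrition a | P, true 15% | P, true 7.5% | Missing, a(1 − q), at 15% |
|---|---|---|---|
| 10% | 15.7% | 7.9% | 9.2% |
| 20% | 16.6% | 8.4% | 18.5% |
| 30% | 17.7% | 9.0% | 27.7% |

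At 30%: (0.105 + 0.0231)/(0.700 + 0.0231) = 0.1281/0.7231 = 17.7%. Only the 30% row passes the 20% trigger for imputation. In the other rows leavers would be dropped, with the same inflation.

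**4. Risk ratio** (true control risk 15%, event-free leavers not counted in either group)

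| Belt / control attrition | True ratio | Estimated ratio |
|---|---|---|
| 30% / 30% | 1.00 | 1.00 |
| 30% / 30% | 0.400 | 7.21/17.72 = 0.407 |
| 30% / 10% (assumed) | 1.00 | 17.72/15.72 = 1.13 |
| 30% / 10% (assumed) | 0.400 | 7.21/15.72 = 0.46 |
| 10% / 30% (assumed) | 1.00 | 15.72/17.72 = 0.89 |

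At 7.5% the three null ratios are 1.00, 1.14 and 0.88.

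**5. Event-free control leavers kept in the denominator.** The control proportion is (1 − a)p + aq = 12.8% at 30% attrition. With belt leavers imputed, the null ratio is 17.7/12.8 = 1.38 (1.41 at 7.5%), against the belt, at equal attrition.

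**6. Cross-check.** A constant exit hazard instead of uniform exit gives 17.6% at 30% attrition and null ratios of 1.12 to 1.13 for belt 30% / control 10%. A simulation at 268/536 with 50 imputations in the belt arm and control leavers dropped gave these one-sided type I errors, against a nominal 2.5%:

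- equal 30% attrition: 1.7% to 2.4%
- control 10%: 0.5%
- control 50% (assumed): 7.7% to 10.8%

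A person-time test stayed at 1.5% to 2.1% throughout.

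**The case against.** **The inflation rests on one reading.** If every subject without a 180-day visit is missing, injured or not, which the wording of SAP 6.3, 6.3.1 and 7.2 allows, missingness no longer depends on the outcome. Under independent exit the inflation disappears and only information is lost. This stands. SAP 3.2.1 is the more explicit statement of the window, but the sections conflict.

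**A reader might infer that the comparison is biased as planned.** The documents do not show that. The only attrition figure, 30%, is applied to both groups in sizing, and equal attrition leaves the ratio almost unchanged if event-free leavers are treated alike. The 10% and 50% control figures are mine. The one mechanism in the documents, voluntary withdrawal from the belt, points to bias against the device; none is stated for the opposite direction.

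**A reader might infer that uninjured control leavers are dropped.** SAP 6.2.2 excludes controls with missing information from the propensity score analysis, whose inputs are age, mobility, sex and a fall in the past year. It does not say that a control who died uninjured counts as missing. The alternative in step 5 is larger, so the silence matters either way.

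**The size depends on the estimand.** The 15% benchmark treats every exit as independent censoring. If every exit were a death and death were a competing event, the target at 30% attrition would be 12.8%, and 17.7% would overstate it by a factor of 1.38. A hazard ratio is a further estimand, and nothing here requires the primary analysis to become one.

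**Conclusion.** The point holds conditionally. What does not depend on a model is that the stated rules allow injuries to be imputed after an uninjured death, ignore recorded event-free time, treat the two groups differently, and leave uninjured control exits unscored.

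If injuries before exit count, reported risks are too high: about 17.7% for a true 15% at 30% attrition, or 9.0% for a true 7.5%. The ratio is nearly unaffected at equal attrition (0.407 against 0.400). It is biased in either direction if attrition differs (null 1.13 or 0.89 in the assumed examples), and against the belt if only the control group keeps its event-free leavers in the denominator (about 1.38). These figures assume constant injury hazard and exits independent of injury; death related to injury risk is not modelled. They do not establish that the trial's result will be biased, because control attrition is not given.

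**What to change.** - State how an uninjured death and an uninjured exit are scored, with one rule for both groups. Impute no injury after death.
- Credit event-free time up to exit. One way is propensity-adjusted cumulative incidence at day 180, with death as a competing event and censoring at withdrawal or discharge. It can be the primary analysis or a prespecified key supporting one, with the imputed proportion kept as a sensitivity analysis.
- Reconcile SAP 6.3 (the imputed analysis is primary) with 6.3.1 (only above 20% missing, as a repeat).
- Reconcile SAP 3.2.1 with 6.3, 6.3.1 and 7.2 on whether injuries before exit count.

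**Cost.** A SAP revision before outcomes are compared. Protocol 14.1 already requires exit dates in subject files. For controls, the documents promise only baseline, midpoint and final metrics from the EMR, so control exit and death dates must be extracted. The estimate becomes a cumulative incidence rather than a simple proportion.

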6.3.1 MULTIPLE IMPUTATION

Prior to propensity score matching, the intervention group may have missing information on the primary endpoint (i.e. major hip injury due to a fall), primarily due to premature withdrawal from the study.

At the time of the final analysis, if more than 20% of data is missing for the primary endpoint reported at the 180-day visit, then the primary endpoint will be multiply imputed and the analysis from section 7.2 will be repeated using both observed and multiply imputed data.

For the multiple imputation, a total of 50 imputed datasets will be calculated (Graham et al.). Fully conditional specification (FCS) logistic regression will be used to impute missing major hip injury due to a fall status (primary endpoint) using the baseline covariates of age, sex, ethnicity, race, mobility level (Independent, Limited Assist, Supervision, Extensive Assist, or Total Dependence), BIMS Score, and FES-I score.

The analysis for the primary endpoint will be carried out utilizing 50 datasets and then results will be combined using PROC MIANALYZE in SAS to obtain one overall test of significance.

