5.2.1 INTENT TO TREAT POPULATION (ITT)

The ITT population will consist of all intervention population subjects who demonstrate at least 64% adherence to use of device during run-in period (defined as wearing device for at least 1 hour per day for at least 9 of 14 days) and the propensity matched historical controls.

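### SAP 6.3 makes the multiply imputed analysis primary without condition, while 6.3.1 makes it a conditional repeat above a 20% threshold whose denominator is not stated

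*Combined protocol and SAP*

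**What the plan says.** - **SAP 6.3** expects substantial loss ("it is anticipated that there will be approximately 30% attrition") and commits to imputation in the ITT population: "The primary effectiveness analysis will be performed on data that has the primary outcome multiply imputed". No condition is attached.
- **SAP 6.3.1** first says whose data may be missing, and when: "Prior to propensity score matching, the intervention group may have missing information on the primary endpoint". It then imputes at the final analysis only "if more than 20% of data is missing for the primary endpoint reported at the 180-day visit". If that condition is met, "the analysis from section 7.2 will be repeated using both observed and multiply imputed data".
- **SAP 5.2.1** defines ITT as the belt subjects who pass the run-in "and the propensity matched historical controls".
- **SAP 6.2.2** allows no imputation for controls: "Control subjects missing information will not be used in the Propensity Score (PS) analysis".
- **SAP 7.2** defines the primary proportion as "the total number of subjects who experience a major hip injury due to a fall divided by the total number of subjects". It tests the hypothesis by logistic regression controlling for propensity score and does not mention imputation.
- **SAP 7.1** matches 1:2 and allows the ratio to move between 1:1 and 1:4 at the final analysis.

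**The concern.** Two sections give different rules for the only primary test, and that test is the gate to all three secondary endpoints (SAP 6.5). Under 6.3 the imputed analysis always decides. Under 6.3.1 it may not be run, and if it is run it is worded as a repeat, which suggests that another analysis came first.

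The missing denominator makes this worse. The same final data can lie above or below 20% depending on which subjects are counted, so the choice could be made after outcomes are known. If imputation is not run, the SAP gives no explicit rule for belt subjects who leave early. Those subjects might be kept in the 7.2 denominator as event-free, dropped by the regression, or dropped only if they left without an injury. These options push the error rate in opposite directions.

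The threshold is tied to the final analysis, so 6.3.1 gives no rule for the interim look, where the trial can stop for success (SAP 4.1).

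**Working it through.** **1. The plan's own attrition figures.** SAP sections 2 and 4 inflate for 30% loss by N/(1 − 0.30):
- interim belt: 94/0.70 = 134.3 (SAP 134)
- final belt: 188/0.70 = 268.6 (SAP 268)
- final control: 376/0.70 = 537.1 (SAP 536)

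These agree to within rounding. The SAP therefore expects about 0.30 × 268 = 80.4 belt subjects without a 180-day outcome.

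**2. The missing share under each denominator.** Let d be the belt loss and k the number of controls per belt subject. By 6.2.2 the matched controls are complete, so the missing share of the matched ITT set is d/(1 + k). It exceeds 20% only if d > 0.20 × (1 + k).

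| Denominator | Missing at d = 30% | Belt loss needed to exceed 20% |
|---|---|---|
| Belt subjects only | 80.4/268 = 30% | 20% |
| Matched ITT, 1:1 | 0.30/2 = 15% | 40% |
| Matched ITT, 1:2 | 80.4/804 = 10% | 60% |
| Matched ITT, 1:3 | 0.30/4 = 7.5% | 80% |
| Matched ITT, 1:4 | 0.30/5 = 6% | not reachable |

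The 536 controls are an attrition-inflated number. If only the 376 complete ones remain, the share is 80.4/(268 + 376) = 12.5%.

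On the belt-only denominator the threshold is met comfortably. With 268 subjects and a true loss of 30%, the probability that at least 54 are missing (more than 20%) is 0.9999. If belt subjects injured before leaving count as observed, at an assumed risk between 1.5% and 15%, the missing share is 0.30 × (1 − 0.015) = 29.6% down to 0.30 × (1 − 0.15) = 25.5%. Both are still above 20%.

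**3. The two sections side by side, belt-only reading.**
- Loss of 20% or less: 6.3 says impute; 6.3.1 says do not.
- Loss above 20%: both impute, but 6.3 calls the result primary and 6.3.1 calls it a repeat of 7.2. Neither 6.3.1 nor 7.2 says which result decides.

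**4. What is at stake if imputation is not run.** This is an illustration under the null. The assumptions, which are not in the SAP, are equal true risk in both groups, exits spread evenly over 180 days, 268 belt subjects against 375 to 536 controls, and a Wald logistic test at one-sided 0.025 without propensity adjustment (400,000 simulated trials).

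At a risk of 15% per 180 days, a leaver's mean risk before exit is 1 − 0.15/(−ln 0.85) = 1 − 0.15/0.1625 = 0.077. At 30% belt loss:
- **Leavers without a recorded injury scored event-free:** belt proportion = 0.70 × 0.15 + 0.30 × 0.077 = 0.128, against 0.15 in controls. False-positive rate about 11% to 12%.
- **All leavers dropped:** belt proportion = 0.15. Rate about 2%.
- **Injured leavers counted, only event-free leavers missing:** belt proportion = 0.128/(0.70 + 0.30 × 0.077) = 0.128/0.723 = 0.177. Rate about 0.2%; the bias runs against the belt.

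SAP section 4 gives 15% as an observed proportion without a time unit, while sections 2 and 4.1 call it annual. At half that, 7.5% per 180 days, event-free scoring gives about 7%. At 20% belt loss, event-free scoring gives about 7% (15% risk) or about 5% (7.5% risk), and counting only injured leavers gives about 0.6% (15% risk).

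**The case against.** The strongest reply is that 6.3.1 supplies its own denominator by context. The sentence just before the threshold speaks of the intervention group, before matching. At that stage the pooled set of 5.2.1 does not yet exist, and controls are never imputed. Read that way, 30% exceeds 20%, imputation runs, and 6.3 and 6.3.1 agree on imputing at the planned attrition. A loss of 20% or less is unlikely, since SAP section 9 raised the assumption from 20% to 30% after about half the belt subjects had exited. The closing words of 6.3.1, on combining the 50 datasets into one overall test, also suggest that the imputed result is meant to decide.

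Most of this stands. A reader might infer from the ITT definition that the threshold cannot be met at 30% belt loss and that imputation is in effect switched off. The documents do not support that: it holds only on the matched ITT denominator, which 6.3.1 does not name and its context does not favour. If the pooled share were taken before incomplete controls are removed, and controls lost 30% as well, about 30% would be missing and the threshold would be met.

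A reader might also take 11–12% as the plan's expected error rate. That needs three things together: imputation not run, leavers scored event-free, and 15% risk per 180 days. The SAP nowhere says that leavers are event-free; 6.3 and 6.3.1 treat early withdrawal as missing data, and a logistic regression would normally omit them.

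The reply does not remove the contradiction. Context is not a definition, 6.3 still carries no condition, and 7.2 still does not mention imputation.

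**Conclusion.** The point holds as a contradiction about which analysis is primary. It does not depend on the choice of denominator: 6.3 is unconditional and 6.3.1 is conditional. The denominator then decides whether imputation runs at the planned 30% belt loss: 30% on belt subjects (threshold met), 10% to 12.5% on the matched ITT set at 1:2, and at most 15% at any permitted ratio (not met). The matched-set shares rest on 6.2.2 leaving the matched controls complete.

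The effect on error is uncertain in direction. Under the stated assumptions at 30% loss, the one-sided rate without imputation runs from about 0.2% through about 2% to a worst case of 11–12% (about 7% at the lower risk). The worst case is not a forecast. The defect is that the SAP leaves the choice open on its only primary test, where it could be settled after outcomes are known.

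**What to change.** In SAP 6.3.1, delete the 20% threshold and the word *repeated*. State that the imputed ITT analysis named in 6.3 is the single analysis that decides the primary endpoint, whatever the amount missing, and that the same rule applies at the interim look. Refer to this from 7.2. Keep the observed-data analysis as a sensitivity analysis, with subjects of unknown status left out of the denominator. If a missing percentage is reported, compute it on belt subjects only.

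Naming the denominator and the deciding analysis while keeping the threshold would also remove the ambiguity, but 6.3 would then need a matching condition. Deleting the threshold is simpler and follows the sponsor's own statement in 6.3.

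The sensitivity analysis should say how an injury recorded before exit is counted. As shown above, keeping injured leavers while omitting uninjured ones leans against the belt.

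The cost is about two sentences of SAP wording and no new data. The change should be made before anyone who decides on it has seen outcomes by group.
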